We are currently studying SGB effects in postmenopausal women in a sham-controlled clinical trial funded by the National Institute on Aging (NIA R01AG049924-01; PI [name]).

Given the frequency and severity and interference of HF in men on ADT for prostate cancer, in addition to the negative effects HF impose on this patient population and a paucity of effective treatments, finding alternative treatments for HF in this population is needed.

STU#:00208657

Version 3.1

11/25/2019

3.0 STUDY ENDPOINTS:

Primary Outcome

Change in frequency of weekly hot flashes by self-report hot flash diary between baseline and 3 months following the intervention.

Secondary Outcomes

1. Change in frequency of weekly hot flashes by self-report hot flash diary between baseline and 1 month following the intervention.
2. Change in frequency of weekly hot flashes by self-report hot flash diary between baseline and 6 months following the intervention.
3. the change in hot flash severity (hot flash frequency * hot flash intensity) between baseline and 1, 3, 6 months following the intervention
4. the change in Hot Flash Related Daily Interference Scale (HFRDIS) between baseline and 1, 3, 6 months following the intervention
5. PROMIS SF4a (sleep)
6. Patient Global Impression of Change Score (PGIC)
7. Number and type of adverse events related to SGB according to NCI-CTCAE v5.0.

Mean frequency= $((F_{mi}+F_{mo}+F_{se})/7)$

where F_{mi} , F_{mo} and F_{se} are the weekly total number of mild, moderate or severe/very severe HF events

Mean severity = $(F_{mi}+2\times F_{mo}+3\times F_{se})/7$

where F_{mi} , F_{mo} and F_{se} are the weekly total number of mild, moderate or severe/very severe HF events In the case of mean severity, frequency of mild vasomotor symptoms (VMS) is not counted at baseline

4.0 STUDY INTERVENTION:

Image Guided Right Sided Stellate Ganglion Block with 0.5% Bupivacaine

5.0 PROCEDURES INVOLVED:

5.1 Study design:

We aim to conduct a single-site, open label trial of SGB in men with prostate cancer on ADT.

5.2 Methods & Study Procedures:

Refer to the Section 5.3, Schedule of Events, for additional information.

Visit 1

Consent

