Participants will be transferred to a recovery area and monitored in a reclining position for approximately 20-30 minutes after the SGB to assess potential adverse effects of the injection. Vital signs will be measured approximately every 5 minutes during the recovery phase. Presence of a Horner's sign (miosis, ptosis, anhydrosis) will be recorded and will validate successful SGB. Expected adverse events and serious adverse events may include any of the following:

Adverse Events (Immediate Post-Procedure):

Local anesthetic toxicity (seizure, loss of consciousness)

Inability to swallow (superior laryngeal nerve spread of local anesthetic)

Difficulty with phonation (recurrent laryngeal nerve spread of local anesthetic)

Weakness of arm (brachial plexus spread of local anesthetic)

Weakness of arms and legs (epidural spread of local anesthetic)

Shortness of breath (phrenic nerve spread of local anesthetic)

These effects would be clinically apparent in the Post-Anesthesia Care Unit (PACU) during the 30 minute post injection observation period; patients are not discharged until vital signs, motor and sensory function of the upper and lower extremities are assessed as normal, and patient is able to phonate and swallow liquids.

STU#:00208657

Version 3.1

11/25/2019

Follow-Up

- 24h follow-up (+3 days to allow for scheduling constraints with weekends)

Participants will be contacted one day following the intervention to assess for any adverse events or side effects. Expected adverse events may include any of the following:

Pain at injection site

Swelling at injection site

Severe bruising at injection site

- Long-term follow-up at 1, 3, and 6 months

Participants will complete daily hot flash diaries and weekly HFRDIS scales via REDcap email for the duration of the 6 month follow up. Secondary measures will be collected at 1, 3 and 6 months after the intervention. Participants will have the opportunity to share any new concerns or problems with research personnel during these interactions, and will be instructed to contact [name] (PI) if any more urgent concerns arise. Contact information is provided in the ICF.

Patients will be contacted via telephone or via REDcap generated email on a weekly basis, if needed, to encourage continued participation in follow up measures, and data will be collected via REDcap. Reminder phone calls will be made if the participant forgets to send their information.

Schedule of Events

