	Screening and Baseline Assessments ⁷	Registration ⁷	Day of Intervention ⁸	1 day follow-up (+ 3 day window)	1 month follow-up (± 7 day window)	3 month follow-up (± 7 day window)	6 month follow-up (± 7 day window)
Informed consent	X						
Demographic information and medical history ¹	X						
Physical exam, height, and weight ²	X						
AE assessment ³	X		X	X	X		
HF severity assessments ⁵	X (collect HF data for ≥ 1 week prior to the day of intervention)				X	X	X
HFRDIS ⁶	X			Weekly during follow-up per Section 5.2			
PROMIS SF4a ⁶	X				X	X	X
PGIC score ⁶					X	X	X
Registration ⁷		X					
SGB Intervention ⁸			X				
Horner's sign assessment post-SGC intervention ⁸			X				
Timed vitals during recovery ⁹			X				
Follow-up contact ¹⁰				X	X	X	X
Weekly reminders ¹¹				X			
Hot flash diary ^{12, 5}				X			

STU#:00208657

Version 3.1

11/25/2019

1. Demographic information and medical history to include: age, body mass index, race, years of education, marital status, Gleason score, duration of hot flashes (months), type of ADT (specify) per Section 5.4. Height and weight to be collected for BMI calculation. Pathology report to be collected to determine Gleason Score.
2. Brief physician-directed physical exam to focus on cervical range of motion and anterior cervical anatomy per Section 5.2.
3. Refer to Section 5.6 for details on the collection of AEs and SAEs. In brief, AEs that are related to the intervention (irrespective of expectedness) will be collected from the time of consent (baseline) through the 30 days after the intervention (the 1 month follow-up visit). All SAEs (irrespective of attribution/relatedness or expectedness) will be collected from the time of consent (baseline) through 30 days after the intervention (the 1 month follow-up visit).
4. Screening labs not required for this study; not a standard of care
5. Patient-reported hot flash (HF) frequency and HF intensity to be collected, based on the participant's hot flash diary. These values will be used to calculate a HF severity score, per Section 3.0. Participants must complete the diary for at least 1 week prior to receipt of the intervention to be able to determine the baseline HF severity score.
6. HFRDIS, PROMIS SF4a, and PGIC score questionnaires to be administered via REDCap. Other methods may also be used (i.e. in person, over the phone, through mail or email, etc.) if required.

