14.0 WITHDRAWAL OF PARTICIPANTS

Patients can be taken off the study treatment and/or the study as a whole at any time at their own request, or they may be withdrawn at the discretion of the investigator for safety, behavioral or administrative reasons. The reason(s) for discontinuation must be clearly documented on the appropriate CRF. An example of when participants may be withdrawn from the research without their consent is if they are non-compliant with providing outcome measures and/or if they begin using a medication known to have an effect on HF. In such cases, or if the participant communicates in writing that he wishes to withdraw, this will be communicated to the study team and the participant and status will be changed from "active" to "inactive".

STU#:00208657

Version 3.1

11/25/2019

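### The weekly total is divided by a constant 7 with no rule for unreturned diary days, so as printed each missing day counts as zero hot flashes

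*Combined protocol and SAP*

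**What the plan says.** Section 3.0 (Study Endpoints) gives two formulas. Mean frequency is the sum of mild, moderate and severe/very severe events divided by 7. Mean severity is the same sum with weights 1, 2 and 3, also divided by 7. The F terms "are the weekly total number of mild, moderate or severe/very severe HF events". Neither formula refers to the number of diary days completed. A note beside the severity formula adds that mild events are not counted at baseline.

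On data collection, Section 5.2 says: "Participants will complete daily hot flash diaries and weekly HFRDIS scales via REDcap email for the duration of the 6 month follow up". It adds: "Reminder phone calls will be made if the participant forgets to send their information". Footnote 11 to the Schedule of Events allows contact about once a week, or less often as needed. Section 14.0 allows withdrawal of men "if they are non-compliant with providing outcome measures", with no threshold.

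For baseline, footnote 5 to the Schedule of Events says: "Participants must complete the diary for at least 1 week prior to receipt of the intervention". Entry also needs about 28 hot flashes per week (at least 28 in Section 5.2, more than 28 in Section 9.0).

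Section 17.0 describes the primary outcome as a mean daily frequency and sets a reduction above 35% as clinically significant. It has no missing-data method. Nowhere do the documents give a minimum number of days for a valid week, a prorating or imputation rule, or a way to tell a blank day from an event-free one.

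**The concern.** A weekly total divided by 7 is a correct daily mean only when all seven days were recorded. When a man returns five days, the events of the other two are absent from the numerator but those days stay in the divisor. The result is the value he would have had with no hot flashes on those two days.

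This affects the frequency endpoints, the severity endpoint and the >35% criterion. The trial has one arm, so no comparison group carries the same error. It also matters for the plan's stated aim of supplying better estimates of frequency and variability for a later randomised trial, because unscored days would distort both.

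**Working it through.** **The plan's own figure.** The Section 17.0 inputs are baseline 46.0 ± 43, follow-up SD 21, difference 23.9, two-sided alpha 0.05 and 80% power.

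- At correlation 0.8, the SD of change is √(43² + 21² − 2 × 0.8 × 43 × 21) = √845.2 = 29.07. The effect size is 23.9/29.07 = 0.822. The exact paired t-test needs n = 14 (power 0.811).
- At correlation 0.7 the SD is 32.03 and n = 17.
- For attrition, 14/(1 − 0.20) = 17.5, rounded up to 18.

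All the stated figures reproduce, and none depends on the present point.

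**Effect of missing days.** Let a man's true rate be unchanged and let m of the 7 follow-up days be unreturned. His recorded total is expected to be (7 − m)/7 of the true weekly total, so the printed formula shows a fall of m/7 at any baseline rate. For a man at 46 per week (46/7 = 6.57 per day):

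| Days missing | Recorded total | Total ÷ 7 | Apparent fall | Total ÷ days returned |
|---|---|---|---|---|
| 0 | 46.00 | 6.57 | 0% | 6.57 |
| 1 | 39.43 | 5.63 | 14.3% | 6.57 |
| 2 | 32.86 | 4.69 | 28.6% | 6.57 |
| 3 | 26.29 | 3.76 | 42.9% | 6.57 |
| 4 | 19.71 | 2.82 | 57.1% | 6.57 |

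The 35% threshold corresponds to 0.35 × 7 = 2.45 days. Three missing days pass it, and four exceed the 52% design effect. A true 20% reduction reads as 1 − 0.8 × 6/7 = 31.4% with one day missing and 1 − 0.8 × 5/7 = 42.9% with two.

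Leaving the total undivided changes nothing: 32.86 against 46 is the same 28.6% fall. The cause is the absence of a partial-week rule. The constant 7 is where it shows in the formulas.

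**Direction.** If a fraction p of days is missing at baseline and q at follow-up, an unchanged mean of 46 gives an expected change of 46(1 − q) − 46(1 − p) = 46(p − q). Equal rates cancel, more missing at follow-up favours the block, and more missing at baseline goes against it.

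**False-positive error, under assumptions.** The documents give no missing-day rate. The simulation took n = 14, no true effect, gamma-shaped weekly counts with mean 46 and SD 43 at both times, a complete baseline, follow-up days missing at random, and a two-sided paired t-test at 0.05. The probability of a significant fall was:

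| Average days missing | Pearson correlation about 0.56 | Pearson correlation about 0.8 |
|---|---|---|
| 0 | 2% | 2% |
| 1 | 8% | 12% |
| 2 | 22% | 38% |

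The nominal rate in that direction is 2.5%. A separate run with latent correlation 0.8 gave 10.7% at one day and 34.6% at two. In that run, an average of 0.5 missing day moved the two-sided error from 4.4% to 5.9%. Falls alone went from 2.2% to 5.2%.

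**The case against.** The strongest reply is that this is an omission and not a rule. F is defined as a weekly total, dividing a true weekly total by 7 is correct, and no sentence says that a missing day is zero. A reader might infer that the plan prescribes zero-scoring. It does not: zero-scoring is what the arithmetic gives when the formula meets a partly returned week. That part of the reply stands. It does not remove the problem, because the formula is the only instruction the analyst has.

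A reader might also infer that the baseline week is guaranteed complete and that the bias is therefore wholly one-sided. The documents do not support that. A diary week is required, but no rule checks that all seven days were returned, and a man with five days and 30 events would still meet the entry count. A fuller baseline is likely, not certain.

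For severity, the exclusion of mild events at baseline pulls the other way if mild events count at follow-up, so a bias in favour of the block cannot be claimed there. Nor does the divisor misfit a baseline diary longer than a week, since F is a weekly total. The open question is which week is used.

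Reminders and discretionary withdrawal should reduce missing days, and the reminder sentence is a safeguard, not a forecast. Neither says how to score the days that remain missing. The simulation also uses SD 43 at follow-up where the plan assumes 21. That is a choice made to represent no effect, and it is one more reason to read the error rates as a range.

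**Conclusion.** The point holds in limited form. Applied as printed to a partly returned week, the formulas lower the value by 1/7 per missing day, and three such days alone exceed the >35% criterion. That is arithmetic and needs no assumption beyond an unchanged rate across days.

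For frequency, the net bias is probably toward apparent benefit, because baseline is better protected than follow-up. Missing baseline days would work the other way. For severity, the net direction is not established.

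The effect on false-positive error depends on missing-day rates that the documents do not give: little change in two-sided error at an average of half a day, about 8–12% significant falls at one day and about 22–38% at two. The point concerns partly returned weeks. A week with no diary at all would presumably make the man non-evaluable, though no rule says so. The plan should be changed before analysis, but the sample-size calculation is not affected.

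**What to change.** Amend Section 3.0, and refer to it from Section 17.0, along these lines:

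- At baseline and at every follow-up, divide the recorded total by the number of diary days completed in the assessment week. Multiply by 7 where a weekly rate is reported.
- Require an explicit zero entry for an event-free day, so that a blank is distinguishable. The intensity scale in Section 5.4 already has a zero category.
- Pre-specify a minimum number of completed days, for example 4 of 7, below which the week is treated as missing. The number is a judgement, so add a sensitivity analysis with a stricter minimum.
- State which seven days form the baseline, 1-, 3- and 6-month weeks.
- Report the number of completed days per man at each time point.

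The cost is a few sentences, a small diary-form setting and one line of code. There are two downsides. A few sparse weeks become missing in a sample of 14. Prorating also assumes that unreturned days resemble returned ones: if men skip the diary on symptom-free days, it would overstate follow-up frequency. The explicit zero is meant to limit that, and the sensitivity analysis should show how much the result depends on it.

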Study Title: Does Stellate Ganglion Blockade (SGB) in Men Treated for Prostate Cancer Improve Hot Flashes? A Pilot Prospective Cohort Study

Study Protocol Version 3.1 11/25 2019

NCT003796195

STU#:00208657

Version 3.1

11/25/2019

PROTOCOL TITLE: Does Stellate Ganglion Blockade (SGB) in Men Treated for Prostate Cancer Improve Hot Flashes? A Pilot Prospective Cohort Study

PRINCIPAL INVESTIGATOR:

[name], MSCI

Department of Anesthesiology

[contact]

[contact]

Co-Investigator

[name], MPH

Department of Medicine, Division of Hematology & Oncology

Statistician

[name]

Department of Anesthesiology

VERSION NUMBER:

3.1

VERSION DATE:

11/25/2019

STUDY SUMMARY:

Special Population(s)	NA
Sample Size	N = 14 is the required number of enrollees who are needed to be evaluable both at baseline and 6 months for the primary outcome. Allowing for dropouts, up to 18 pts might be enrolled
Funding Source	Internal funding
type of consent to be obtained	Written
Site	Single Site
Research Related Radiation Exposure	Yes

STU#:00208657

Version 3.1

11/25/2019

1.0 OBJECTIVES:

Scope: Men with prostate cancer with or without metastatic disease treated with androgen deprivation therapy for at least 2 months, with bothersome refractory hot flashes, will be enrolled as participants in this open label clinical trial.

Aim 1: To determine the effect of stellate ganglion blockade (SGB) for reducing hot flash frequency and severity in men with prostate cancer in the 6 months following the intervention.

Aim 2: To evaluate the effect of SGB on daily hot flash (HF) interference and sleep quality.

Hypotheses: Hot flash frequency, interference and sleep quality will be improved in men following stellate ganglion blockade with local anesthetic.

2.0 BACKGROUND:

Androgen Deprivation Therapy (ADT) is a critical component of advanced prostate cancer treatment but causes numerous adverse effects including decreased bone mass, decreased muscle mass, gynecomastia, erectile dysfunction, loss of sexual desire, depression, disordered sleep, urinary symptoms, and hot flashes (HF)(1). HF are unpleasant paroxysmal episodes of flushing, sweating with vasodilation of the face, neck, and chest. These episodes can last for seconds to minutes and are often associated with night sweats, anxiety, and insomnia and have negative effects on quality of life (9).

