Stellate ganglion blockade (SGB) with local anesthetic may be an effective treatment of HF in men on ADT, but has not been studied in any published clinical trials. The stellate ganglion is a neural structure in the anterior cervical spine region and is part of the sympathetic nervous system. It has been injected safely in the practice of pain management for more than 50 years in cases of post herpetic neuralgia (shingles), complex regional pain syndrome (CRPS) and other painful neuropathies as well as some types of cardiac dysrhythmias. We recently published a prospective, randomized, sham controlled study of SGB in women with natural or surgical menopause, in which we found a 52% decrease in moderate to very severe HF in women who underwent a single SGB with bupivacaine, a local anesthetic, as compared to a 13% decrease in women in the sham control group who underwent an injection of saline. (20).

Another controlled study of SGB in women with breast cancer on endocrine therapy confirmed considerable reductions in frequency and intensity of HF in patients who had SGB (21). Uncontrolled studies of women with breast cancer and heterogeneous populations including postmenopausal women have demonstrated improvements in the frequency and intensity of HF following SGB, with 45-90% reduction in HF frequency or intensity, for durations ranging from 4 weeks to several months (22-24). Together, this literature provides further support of the hypothesis that SGB could be beneficial to men on ADT.

The mechanism of SGB mitigation of HF in men is unclear. The effects of testosterone on prevertebral ganglia are widely variable (25). Anatomic connections between the stellate ganglion and thermoregulatory regions in the brain via third order neurons have been described (26). SGB interrupts the sympathetic nervous system and may modulate norepinephrine levels in these thermoregulatory regions. Androgen deprivation as in ADT appears to change NE levels and activate the sympathetic nervous system in rat models (27), but the detailed interaction between testosterone and NE levels in humans is unclear (25, 28, 29). Some authors have alternatively hypothesized that Nerve Growth Factor (NGF) levels are modulated following SGB (30, 31), and there is evidence that NGF levels may decrease with testosterone withdrawal, affecting neural growth and neural plasticity (32, 33) that could ultimately effect thermoregulation.

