5.4 Outcome Measures

Hot Flash Diary

Daily Hot Flash Diaries (daily throughout entire study): daily diaries include measures of: (a) hot flashes frequency while awake; (b) the number of night sweats; (c) intensity of hot flashes while awake, with

0 = none

1 = mild (1 or 2 episodes of heat)

2 = moderate (3 to 4 episodes of heat with discrete sweating)

3 = severe (5 or more sudden episodes of heat accompanied by sweating, sleep disturbance, feelings of irritation or anxiety).

Hot Flash Related Daily Interference Scale (HFRDIS)(34)

This validated measure assesses the impact of hot flashes on overall quality of life as well as on work, social activities, leisure activities, sleep, mood, concentration, relations with others, sexuality, and enjoyment of life. A total of 10 areas are assessed with a 0-10 scale. The maximum score, demonstrating the most severe interference of HF is 100.

PROMIS SF4a (sleep)

One of the PROMIS measures, this is a 4-item questionnaire that queries sleep duration, quality, and interruption.

Patient Global Impression of Change

This outcome has the participant assess how much improvement they believe they have experienced from an intervention. This will be collected at 1, 3, and 6 month time points.

General Demographic and Health Status Information

We will obtain sociodemographic and clinical variables based on participant report, including

- age
- body mass index
- race
- years of education
- marital status
- Gleason score
- duration of hot flashes (months)
- type of ADT (specify)

5.5 SGB Risks & Safety:

Stellate ganglion injections are commonly performed in the U.S., have been in clinical use for more than 50 years, and are considered safe and effective in treating a variety of neuropathic syndromes and ischemic pain states and cardiac dysrhythmias (Complex Regional Pain Syndrome Type I and II, herpes zoster, frostbite, Raynaud's syndrome, vascular headaches, refractory ventricular tachycardia, pulmonary artery hypertension, for example). Several more recent studies have demonstrated clinical effectiveness in treating vasomotor symptoms

STU#:00208657

Version 3.1

11/25/2019

in women and no adverse events have been reported from these more recent trials.

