Nominal patient characteristics data will be summarized descriptively as number and percent of participants in each category. Ordinal and continuous patient data that are not approximately normally distributed will be summarized as median and interquartile range (IQR). Normally distributed continuous patient data will be presented as mean \pm SD.

STU#:00208657

Version 3.1

11/25/2019

Data required for the primary outcome variable, i.e., mean daily frequency of severe hot flashes in the study sample at 6 months after the intervention vs. the baseline daily frequency of hot flashes in the study sample, will be reported as the mean \pm SD if appropriate, or as the median (IQR) otherwise. The primary outcome data will be evaluated using a paired t-test if the data are approximately normally distributed, or using with the Wilcoxon matched pairs signed rank test if they are not. The mean difference and 95% CI will be calculated. The criterion for rejection of the null hypothesis (i.e. no change over the baseline to 6-month follow-up assessment of the mean weekly frequency of severe hot flashes) will be a two-tailed $p < 0.05$.

For AE analysis, safety and tolerability will be summarized descriptively by providing the frequency of adverse events by severity, type, and attribution.

Differences from baseline and associated 95% CIs will be calculated for planned analyses. Variables that are approximately normally distributed (e.g., hot flash frequency) will be summarized as mean \pm SD. These data at baseline, 1, 3, and 6 months will be compared using the one-way repeated measures analysis of variance with pairwise multiple comparison with baseline made using the Holm-Sidak method when appropriate.

The criterion for rejection of the null hypothesis for all of the secondary analyses will be a two-tailed $P < 0.05$, as this is an exploratory study.

With severe HF frequency selected as the primary outcome, $> 35\%$ reduction from baseline to 6 months will be considered to be clinically significant. However, as this is an exploratory study, a larger reduction was used for the power analysis presented above.

If this study shows meaningful treatment effects in this study population, we plan to further evaluate our hypotheses in a larger, randomized blinded sham controlled study.

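### The severity score leaves out mild hot flashes at baseline but not at follow-up, which shifts the change in severity toward worsening

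*Combined protocol and SAP*

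**What the plan says.** Section 3.0 (Study Endpoints) lists as secondary outcome 3 "the change in hot flash severity (hot flash frequency * hot flash intensity) between baseline and 1, 3, 6 months following the intervention". Below the list it gives two formulas:

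- Mean frequency = (F_mi + F_mo + F_se)/7
- Mean severity = (F_mi + 2F_mo + 3F_se)/7

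The three F terms "are the weekly total number of mild, moderate or severe/very severe HF events". One sentence then applies to severity only: "In the case of mean severity, frequency of mild vasomotor symptoms (VMS) is not counted at baseline". The frequency formula has no such exception.

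Nothing elsewhere completes or reverses the rule. Footnote 5 of the Schedule of Events says of the diary values: "These values will be used to calculate a HF severity score, per Section 3.0". Section 17.0 gives no other definition of severity. It says: "Differences from baseline and associated 95% CIs will be calculated for planned analyses".

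**The concern.** A change score needs the same measure at both ends. As written, a mild flash has weight 0 at baseline and weight 1 afterwards. That mild flashes count at follow-up is inferred from the unmodified formula, but it is what the text yields.

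Aim 1 in Section 1.0 is about "reducing hot flash frequency and severity in men with prostate cancer in the 6 months following the intervention". In Section 3.0's list, outcome 3 is the only outcome that scores severity. The trial has one arm, so the mismatch goes straight into the estimated change and its confidence interval. Entry depends on a weekly flash count with no minimum intensity, so men with mild flashes can enrol.

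The rule also penalises a plausible form of benefit. If severe flashes become mild ones, those mild flashes add to the follow-up score although mild flashes counted for nothing at baseline.

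**Working it through.** The plan states no figure for this outcome, so there is none to reproduce.

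**Inputs.** The formula, its weights (1, 2, 3) and the baseline exception come from Section 3.0. The baseline mean of 46 severe flashes a week and the 52% reduction (to 22.1) come from the power analysis in Section 17.0. All other weekly counts are assumptions, because the documents give no breakdown by grade. Counts are written mild/moderate/severe.

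**1. Size of the shift.** With B for baseline and F for follow-up:

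- As written: (mi_F + 2mo_F + 3se_F)/7 − (2mo_B + 3se_B)/7
- Mild counted throughout: the same minus mi_B/7, so the shift is +mi_B/7
- Mild left out throughout: the same minus mi_F/7, so the shift is +mi_F/7

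Either shift is zero only when that mild count is zero. Seven mild flashes a week give +1.0 point; 14 give +2.0.

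**2. A man whose symptoms do not change, each flash graded separately.** The apparent rise is mi/(2mo + 3se).

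| Weekly counts | Baseline | Follow-up | Apparent change |
|---|---|---|---|
| 0/14/14 | 70/7 = 10.00 | 70/7 = 10.00 | 0% |
| 14/14/46 | 166/7 = 23.71 | 180/7 = 25.71 | +8.4% |
| 7/10/11 | 53/7 = 7.57 | 60/7 = 8.57 | +13.2% |
| 14/14/18 | 82/7 = 11.71 | 96/7 = 13.71 | +17.1% |
| 10/10/8 | 44/7 = 6.29 | 54/7 = 7.71 | +22.7% |
| 14/7/7 | 35/7 = 5.00 | 49/7 = 7.00 | +40.0% |

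The mixes that total 28 meet the entry threshold in Section 5.2 (28 or more) but not the one in Section 9.0 (more than 28).

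**3. A small improvement, 14/14/18 to 14/14/14.**

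- Mild counted throughout: (84 − 96)/7 = −1.71
- Mild left out throughout: (70 − 82)/7 = −1.71
- As written: (84 − 82)/7 = +0.29

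**4. A large improvement, 14/14/46 to 14/14/22.**

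- Mild counted throughout: (108 − 180)/7 = −10.29
- Mild left out throughout: (94 − 166)/7 = −10.29
- As written: (108 − 166)/7 = −8.29

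**5. Flashes becoming milder, 0/14/14 to 14/7/7.**

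- Mild counted throughout: (49 − 70)/7 = −3.0
- Mild left out throughout: (35 − 70)/7 = −5.0
- As written: −3.0, so here the shift exists against the second rule only

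**6. Diary grade read as a grade for the day.** The scale in Section 5.4 grades by number of episodes; its lowest symptomatic grade is "1 = mild (1 or 2 episodes of heat". If every flash takes its day's grade (1–2 mild, 3–4 moderate, 5 or more severe), the results for an unchanged man are:

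- 4 flashes every day: 0/56 = 0%
- Days of 2, 2, 2, 6, 6, 6, 6: 6/(3 × 24) = 8.3%
- Largest value: six days of 2 and one of 16, 12/(3 × 16) = 25.0%

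The maximum comes from enumerating all 409,286 unordered seven-day patterns with 0 to 28 flashes a day and 28 to 60 a week. Under this reading an eligible man has at most 12 mild flashes in the baseline week, since seven days of 2 total only 14. The mixes in steps 2 to 4 that contain mild flashes at baseline therefore apply to per-flash grading only.

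**The case against.** The strongest objection concerns size. The reversal in step 3 involves a small effect: 46 to 42 flashes is −8.7%. Section 17.0 treats a reduction of more than 35% in severe-flash frequency as clinically significant. If every grade falls by 35%, all the mixes with mild flashes in step 2 still improve as written: 14/14/46 by 7.0 points, 14/14/18 by 2.8, 7/10/11 by 2.0, 10/10/8 by 1.3 and 14/7/7 by 0.45. At that effect a reversal needs mi/(2mo + 3se) above 0.35/0.65 = 54%, beyond any mix shown. This stands: for effects the plan cares about, the error mainly attenuates. For 14/7/7, though, a true 35% fall (1.75 points on 5.00 with mild left out throughout) is reported as 0.45 points, or 9%.

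Men must also have bothersome refractory flashes and an HFRDIS score above 40 (Sections 1.0 and 12.1), which makes weeks dominated by mild flashes less likely without excluding them. The mix built on the plan's own 46 severe flashes gives only +8%. That limits the likely size.

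The authors may have meant to leave mild flashes out at every visit. Section 2.0 reports their earlier trial in women that way: "we found a 52% decrease in moderate to very severe HF in women who underwent a single SGB". But the sentence names baseline only, and the formula keeps a mild term that would then serve no purpose. An analyst who guesses the intent could defend either of two scores.

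Finally, this is one secondary outcome in a study that calls itself exploratory, and Section 17.0 analyses severe-flash frequency, which carries some severity information and is untouched. Both points bear on priority, not on whether the rule is wrong.

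**Conclusion.** The concern holds. The upward shift follows from the printed formula and needs no assumption: a man's baseline mild count over 7 against one consistent rule, or his follow-up mild count over 7 against the other. A man with mild flashes at baseline and none later is shifted only against the first rule.

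The size in this trial is unknown. On assumed counts, an unchanged man shows a rise of 0% to 40% with per-flash grading, and of 0% to 25% with daily grading.

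The shift cannot move an individual or mean change toward benefit. Because it varies between men, it can raise or lower the SD of the change, so its effect on the p-value is not fixed in direction. It is confined to secondary outcome 3. It should be fixed before analysis, but it does not threaten the frequency outcomes or the sample size.

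**What to change.** Replace the sentence in Section 3.0 with one rule that applies at baseline and at 1, 3 and 6 months. Either count mild flashes at every time point, or set F_mi to zero at every time point and call the result a moderate-to-severe score. Make the choice before the follow-up data are analysed and repeat it in Section 17.0.

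The cost is one sentence. Neither rule adds a measurement: leaving mild flashes out at baseline already requires identifying them, and the follow-up formula already uses F_mi.

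While editing, it would help to state how counts by grade are derived. Section 5.4 lists a daytime frequency, a night-sweat count and a daytime intensity rating, but no counts by grade. That is a separate clarification, and the finding does not depend on it.
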